8.5. Pharmacodynamics Analysis Set

The Pharmacodynamics Analysis set will consist of all subjects in the Safety Analysis set who have measurable post-baseline PD data. For analysis purposes, subjects will be analyzed according to randomized treatment group. The analysis set will be used for all PD data other than MRI and Fibroscan measures. This set will be used for correlation analysis.

8.6. Pharmacodynamics Analysis Set - MRI

The Pharmacodynamics Analysis set – MRI will consist of all subjects in the Safety Analysis set who have measurable post-baseline MRI assessment. For analysis purposes, subjects will be analyzed according to randomized treatment group. This set will be used for MRI related endpoints.

8.7. Pharmacodynamics Analysis Set - Fibroscan

The Pharmacodynamics Analysis set – Fibroscan will consist of all subjects in the Safety Analysis set who have measurable post-baseline Fibroscan. For analysis purposes, subjects will be analyzed according to randomized treatment group. This set will be used for Fibroscan related endpoints.

9. Statistical Methods of Data Analyses

9.1. General Considerations

In general, placebo subjects from each cohort will be pooled for summary.

9.1.1. Statistical Notation and Presentation

All data collected from all subjects in the electronic data capture will be presented in the subject level listings. All continuous data will be listed with the same precision as presented in the database. Data listings will be sorted by cohort, treatment group, subject ID and time point. Missing values will be represented by an empty cell and no imputation will be made. If imputation is used for analysis, excluding treatment-emergent and concomitant medication determinations, the imputed values will be listed with a derivation type column in the listing indicating that origin of the imputed value.

Continuous data will be summarized in tables using number of subjects or sample size (n), mean, median, standard deviation (SD), minimum and maximum. For logarithm-transformed data, the geometric mean, standard error (SE) of the geometric mean and geometric coefficient of variation (CV%) will also be provided.

Categorical data will be summarized in two ways, by subject and by time point. Subject data will be summarized using the count of distinct subjects that fall in the category and the percentage of the total number of subjects. Population counts, either the number of subjects or the number of assessments at the time point, will be used as the denominator in the calculation of percentages unless specified otherwise.

The original units (conventional) and SI units will be presented in listings. In general, conventional units will be used for tables and figures, unless otherwise specified. Insulin will use the conventional unit of uU/mL; estimated glomerular filtration rate will be presented using SI units.

Minimum and maximum values will use the precisions of the original value. Means, least squares (LS) means, and medians will be rounded to one decimal place greater than the precision of the original value up to a max of two decimal places. The limits of confidence intervals, standard deviations and standard errors will be rounded to two decimal places greater than the precision of the original value. Derived PK and PD data will be presented with three significant figures. Percentages will be rounded to the nearest tenth. Two-sided p-values will be presented with four decimal places and values less than 0.0001 will be presented as <.0001.

9.1.2. Statistical Modeling Methods

A mixed model repeated measures (MMRM) analysis will be used to analyze the change from baseline and/or percent change from baseline in the pharmacodynamic endpoints. The model will include baseline as a covariate, treatment group, visit, and the interaction between treatment group and visit as factors. The covariance will be unstructured; if the model fails to converge, other structures such as compound symmetry will be considered. The LS means and the LS mean difference will be presented by visit with their corresponding standard error, p-values and two-sided 90% and 95% confidence intervals.

If strong evidence exists that the normality assumptions are violated for, but not limited to, triglycerides or MRI-PDFF, non-parametric methods will be considered such as the Wilcoxon Rank Sum test.

There will be no adjustments for multiplicity in this study.

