3.5. Sample Size and Power

No formal sample size calculation was performed for the primary endpoint(s) as the total of approximately 83 subjects, consisting of 6:2 (Cohort 1), 12:3 (Cohort 2), 9:3 (Cohorts 4 and 6) or 14:4 (Cohorts 3 and 5) receiving active: placebo, respectively is considered adequate to inform on the endpoints for this Phase 1b study.

A power assessment based on magnetic resonance imaging – proton density fat fraction (MRI-PDFF) endpoint (percent change from baseline to End of Treatment in liver fat content, an important biomarker) shows that 9, 12 and 14 subjects in a dose cohort compared to the pooled 19 placebo subjects will provide [REDACTED] power, respectively, to detect a difference in mean percentage change from baseline between treatment groups of [REDACTED], assuming

a standard deviation of █ in each group. Calculation was based on two-sample one-sided t-test with alpha at 0.05 (e.g., two-sided alpha at 0.10).

Subjects who withdraw from the study before the Day 50 assessments may be replaced at the discretion of the Sponsor.

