Measurements from all protocol planned visits will be summarized in descriptive tables and figures. For pharmacodynamic endpoints that are analyzed using MMRM analysis, only measurements taken at weekly analysis visits (eg, Day 1, Day 8, 15, 22, 29, 36, etc) will be included in the analysis and corresponding data presentation. Analyses will utilize the measurements taken at the scheduled visits whenever they are available. If not available, the analysis will use the measurement mapped to that scheduled visit (whichever is the closest to the target date, and if there are two measurement before and after the target day with same duration, use the measurement taken at the later day) If there are duplicate results from the same sample are available, eg, with the identical sampling date and time, the average value will be used for data analysis and both raw data and average value will be listed. EOS/ET visits will be summarized in descriptive summary. ET visits will be eligible to be mapped to missing protocol planned visits, but will not on its own be considered an analysis visit or time point.

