- m. Vital signs include supine blood pressure, pulse, body temperature, and respiratory rate; vital signs will be measured pre-dose (prior to scheduled blood draws and study intervention administration); 1, 12 and 24 hours post-dose and prior to discharge on domiciled dosing visits (1st and 5th doses); on dosing ambulatory visits, vital signs will be measured pre-dose (prior to scheduled blood draws and study intervention administration) and prior to discharge; on non-dosing visits, vital signs will be measured prior to scheduled blood draws. Starting from randomization, blood pressure and pulse will be measured in duplicate, the first measurement will be taken up to 15 minutes before the indicated time point. Additional vital signs measurement may be done if clinically indicated. Subjects must be in a supine or semi-erect/seated position and resting for at least 5 minutes prior to measurements.
- n. Study intervention will be administered SC to the abdomen region by qualified study personnel.
- o. PK blood samples will be collected as shown in [Table 3](#). Additional blood samples for PK analysis may be collected if clinically indicated (e.g., in case of SAE). For PK sample collection instruction/procedures, refer to the relevant manual.
- p. Blood samples for OGTT test will be collected under fasting conditions (10 hours) at the following timepoints: 0 minutes (just prior to ingesting glucose), 30 minutes, 60 minutes, 90 minutes 120 minutes and 180 minutes. On Day 92/ET the insulin will be captured from the OGTT.
- q. At Screening, MRI-PDFF to be done within 35 days of baseline (Day 1). On Days 50 and 92, MRI-PDFF to be done within \pm 2 days of the planned visit date. If out of the window, MRI-PDFF should still be performed as close to the target day as possible, but protocol deviation should be recorded.
- r. Samples for carboxy-terminal collagen crosslinks (CTX) and N-terminal propeptide of type 1 collagen (P1NP) will be obtained at the designated timepoints for storage and potential future analysis. The D42 sample will be obtained pre-dose.
- s. Samples for RNA as well as plasma and serum samples will be collected for potential future exploratory assessments, to increase understanding of BIO89-100 biological activity and to identify potential existing and/or emerging biomarkers.
- t. [REDACTED]

- u. Immunogenicity sample on Day 92/ET will only be collected for subjects who early terminate from the study.

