13.1. Sample SAS Code

Sample SAS Code for MMRM analysis:

```
proc mixed data=indata;
class trt visit;
model chg /*or pchg*/ = base trt visit trt*visit/ ddfm=kr s;
repeated visit/type=UN subject=usubjid;
lsmeans trt*visit/pdiff cl alpha=0.1;
run;
```

Sample SAS Code for MMRM analysis with Fibrosis Status Y/N as factor:

```
proc mixed data=indata;
class trt visit biopsy_confirmed_NASH_yn;
model chg /*or pchg*/ = base trt visit biopsy_confirmed_NASH_yn trt*visit/
ddfm=kr s;
repeated visit/type=UN subject=usubjid;
lsmeans trt*visit/pdiff cl alpha=0.1;
run;
```

Sample SAS Code for Wilcoxon Rank Sum Non-Parametric analysis:

```
proc npar1way data=indata wilcoxon alpha=0.1;
class trt;
var chg /*or pchg*/;
exact wilcoxon;
run;
```

Sample SAS Code for Hedges-Lehman Estimation:

```
proc npar1way data=indata hl alpha=0.1;
class trt;
var chg /*or pchg*/;
exact hl;
run;
```

Sample SAS Code for Multiple Imputation Using Control Based Pattern-Mixture Model:

```
proc mi data = non_mono out=monotone niimpute=100 seed=123;
var trt01pn day50 day92;
mcmc chain = multiple impute=monotone;
run;
```

Note: Data needs to be in wide format for the multiple imputation procedure Also, dummy variables are need for categorical factors with more than two levels such as TREATMENT.

```
proc mi data=monotone out=imputed1 nimpute=1 seed = 124;
by _imputation_;
class trt01pn;
var trt01pn day50 day92;
monotone reg(/details);
mnar model (day50 day92/modelobs=( trt01pn ='0')) ;
run;
```

```
proc mixed data=imputed;
by _imputation_;
class subject trt visit;
model pchg = base trt visit trt *visit/ddfm=kr;
repeated visit / sub=subject type=un;
lsmeans trt *visit/pdiff cl;
ods output lsmeans=lsmeans diffs=diffs;
run;
proc sort data=lsmeans;
by trt visit _imputation;
run;
proc mianalyze parms=lsmeans;
modeleffects trt * visit;
ods output parameterestimates=lsm;
by trt visit;
run;
proc sort data=diffs;
by visit _imputation;
run;
proc mianalyze parms=diffs;
modeleffects trt * visit;
ods output parameterestimates=dif;
by visit;
run;
```

BIO89-100-002 (Part 2)
NCT #: NCT04048135

Page 1 of 41

Statistical Analysis Plan

[figure not shown]
Protocol BIO89-100-002 (Part 2, Single Cohort)

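### The Part 1 MMRM fits one baseline slope to all visits; a baseline-by-visit term would cheaply protect the precision of the Day 92 comparisons for frequently sampled endpoints

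*SAP*

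**What the plan says.** SAP Part 1, Section 9.1.2, uses an MMRM for change and percent change in the pharmacodynamic endpoints: "The model will include baseline as a covariate, treatment group, visit, and the interaction between treatment group and visit as factors". LS means and their differences are reported by visit, with standard errors, p-values and 90% and 95% intervals. On the covariance it says: "The covariance will be unstructured; if the model fails to converge, other structures such as compound symmetry will be considered".

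The sample code in Section 13.1 matches the text. The main model line is "model chg /*or pchg*/ = base trt visit trt*visit/ ddfm=kr s" and the model run after multiple imputation is "model pchg = base trt visit trt *visit/ddfm=kr". The version with fibrosis status adds only one more main effect. No available text adds a baseline-by-visit term.

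Section 9.1.3 says which visits enter the fit: "only measurements taken at weekly analysis visits (eg, Day 1, Day 8, 15, 22, 29, 36, etc) will be included in the analysis". MRI-PDFF has far fewer. Footnote q of the schedule of activities in the SAP appendix reads "On Days 50 and 92, MRI-PDFF to be done within" two days of the planned date, so it has two post-baseline visits.

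Section 3.5 gives the group sizes: "consisting of 6:2 (Cohort 1), 12:3 (Cohort 2), 9:3 (Cohorts 4 and 6) or 14:4 (Cohorts 3 and 5) receiving active: placebo".

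**The concern.** A model that reports a treatment difference at each visit, but shares one baseline coefficient across visits, adjusts fully at a given visit only if that coefficient is right there. In repeated measurements the correlation with baseline often fades over time, so change depends on baseline more strongly at later visits. With an unstructured covariance, the common slope is a weighted average of the visit slopes that favours the early, less variable visits. The compound-symmetry fallback changes the weights but still allows only one slope.

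The groups are small: 6 to 14 active subjects per dose against 19 pooled placebo. Chance baseline imbalance can therefore be sizeable, and the baseline covariate is the main protection against it. Whatever the common slope leaves unadjusted at Day 92 goes into the LS mean difference as extra variability. The endpoints exposed are those with many early visits: body weight, lipids and ALT/AST.

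**Working it through.** **Plan figures.** The SAP gives no precision figure for this model, and the power, difference and SD in Section 3.5 are blacked out, so there is nothing to reproduce beyond the cell sizes. Active: 6 + 12 + 14 + 9 + 14 + 9 = 64. Placebo: 2 + 3 + 4 + 3 + 4 + 3 = 19. Total 83, as stated.

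**Assumptions (not in the documents).** Outcomes are normal with SD 1 at every visit, and data are complete. The correlation between measurements t days apart is (1 − m)·r^(t/92), where r is the underlying Day 92 correlation with baseline and m the share of measurement noise. The slope of change on baseline at Day k is then (1 − m)·r^(k/92) − 1, the same in all arms. Laboratory visits are taken as Days 8, 15, 22, 29, 36, 50, 71 and 92, because the day headers of the schedule are blacked out. MRI visits are Days 50 and 92.

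**Formulas.** With visit slopes b_k and residual covariance V, the common slope is b = (1′V⁻¹b_k)/(1′V⁻¹1). If d is the true Day 92 slope minus b, and ρ is the Day 92 correlation with baseline, then approximately

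- variance with visit-specific slopes: (1/n₁ + 1/n₂)(1 − ρ²)
- variance with a common slope: (1/n₁ + 1/n₂)(1 − ρ² + d²)

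**Example by hand, r = 0.6, m = 0, 14 versus 19.** The Day 8 slope is 0.6^(8/92) − 1 = −0.04 and the Day 92 slope is −0.40. In simulation about 0.35 was left unadjusted, so the common slope is about −0.05, close to the Day 8 value. 1/14 + 1/19 = 0.124. Visit-specific SE = √(0.124 × 0.64) = 0.282. Common-slope SE = √(0.124 × (0.64 + 0.35²)) = 0.308. Variance ratio = 0.7625/0.64 = 1.19.

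**Simulation.** 3,000 trials per row with the planned group sizes; Day 92 difference, 14 versus 19:

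| Visits | r | m | SE, common slope | SE, base*visit | Variance excess | Left per 1 SD of imbalance |
|---|---|---|---|---|---|---|
| 8 (labs) | 0.8 | 0 | 0.221 | 0.213 | 8% | 0.18 |
| 8 | 0.8 | 0.2 | 0.274 | 0.273 | 1% | 0.10 |
| 8 | 0.6 | 0 | 0.310 | 0.286 | 17% | 0.35 |
| 8 | 0.6 | 0.2 | 0.316 | 0.310 | 4% | 0.19 |
| 8 | 0.4 | 0 | 0.358 | 0.321 | 24% | 0.46 |
| 8 | 0.4 | 0.2 | 0.348 | 0.332 | 10% | 0.32 |
| 8, constant correlation 0.7 | – | – | 0.249 | 0.250 | −1% | 0.02 |
| 2 (MRI) | 0.8 | 0 | 0.213 | 0.211 | 1% | 0.08 |
| 2 | 0.6 | 0 | 0.286 | 0.283 | 2% | 0.13 |
| 2 | 0.4 | 0 | 0.318 | 0.314 | 3% | 0.16 |

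The hand calculation agrees with the third row. In every scenario the common-slope estimate averaged within 0.01 SD of the true value.

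**Conditional error.** One standard error of baseline imbalance for 9 versus 19 is √(1/9 + 1/19) = 0.405 SD. With d = 0.35 this leaves 0.405 × 0.35 = 0.14 SD in the difference.

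**Slopes set directly, 9 versus 19, several assumed residual covariances.** For slopes from −0.10 (Day 8) to −0.50 (Day 92) in all arms, the variance excess was about 6% to 26%. If the slope steepens only in the active arms, it was about 2.5% to 9%. For −0.20 to −0.40 it was about −1% to 6%. With equal slopes, the extra term cost about 0% to 2%.

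**The case against.** The strongest reply is that the loss is conditional and the documents never meet the condition. They give no visit correlations or slopes. With equal slopes the planned model adjusts fully and is marginally more precise. That stands.

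A reader might infer from Protocol Section 2.3.3 that the condition is shown, since triglycerides fell by up to 28% overall but up to 49% in the 15 subjects with high baseline. Those are maxima over doses with no comparison by visit. They suggest that change depends on baseline, not that the dependence grows from Day 8 to Day 92.

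If slopes steepen because the drug effect builds up, placebo subjects should not show it. The slope would then differ by arm, which a baseline-by-visit term shared by all arms only partly captures, and the gain shrinks as shown above. Fading correlation, by contrast, acts in every arm.

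The scope is also limited. MRI-PDFF, the endpoint of the power assessment, is barely touched. Most metabolic markers are sampled at only a few visits, so the eight-visit results do not represent them. SAP Section 9.4.2.3.1, a sensitivity analysis for liver biomarkers, is listed in the contents but its text was not available, so it may already bear on ALT/AST.

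Finally, the stakes are modest. The primary endpoints are safety and PK (SAP Section 4.1), the pharmacodynamic p-values are descriptive (Protocol Section 8.1), and there is no multiplicity adjustment. What remains is the asymmetry: a small cost if the term is not needed, a moderate gain if it is.

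**Conclusion.** The documents establish that Part 1 imposes one baseline slope on all visits in each MMRM while reporting differences by visit. They do not establish that the Day 92 differences are in fact under-adjusted; that depends on slopes differing between visits. Nor is there a case for bias: over randomization the estimates are centred correctly, and the effect is on conditional adjustment and precision.

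Under the assumed slopes, the Day 92 variance excess for body weight, lipids and ALT/AST is about 0% to 25%. It is at the low end if measurement noise is appreciable or if only active arms steepen. For MRI-PDFF it is about 0% to 3%. These figures assume complete, normal data; percent change was not simulated separately. This is a worthwhile precision improvement for secondary, descriptive endpoints, and the planned model is not an error.

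**What to change.** In SAP Part 1 Section 9.1.2, add the baseline-by-visit interaction to the MMRM. In Section 13.1, change the fixed effects to `base trt visit trt*visit base*visit`, and add the same term to the fibrosis-status and post-imputation models for consistency.

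The cost is one degree of freedom per extra visit and about 1% to 2% of variance if the slopes are equal. No new data are needed and the treatment contrast is unchanged.

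Protocol Section 2.3.3 reports that preliminary Part 1 results are already available. If the planned model has been run, show the extended model beside it as a sensitivity analysis for body weight, lipids and ALT/AST, and document it in the study report as SAP Section 1 requires for deviations.

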9.1.3. Analysis Visits and Visit Windowing

In general, all scheduled visits will be used as analysis visit for descriptive analysis tables and listings.

If a scheduled visit is missing, an unscheduled visit may be mapped to take its place if and only if it is within the visit window of the missing scheduled visit. The following table describes the visit mapping of unscheduled post-baseline visits in the event that a scheduled visit is missing. If there are multiple unscheduled visits, the closest one to the projected date will be selected; if there are ties, the later measurement will be used.

| Parameter | Analysis Visit/Time Point Window |
|--------------------------|---|
| Labs | Study Day \pm 3 days from Target Day ET visits are mapped to the nearest missing analysis visit, using the same window, after unscheduled visits are considered. |
| MRI; Fibroscan | Day 50: $36 \leq$ Study Day ≤ 64 (± 14 Days); Day 92: Study Day ≥ 78 ; ET visits within Study Day < 65 will be mapped to Day 50; ET visits with Study Day ≥ 65 will be mapped to Day 92. |
| Vital Signs | Study Day \pm 3 days from Target Day; ET visits are mapped to the nearest missing analysis visit, using the same window, after unscheduled visits are considered. |
| Anthropomorphic Measures | Study Day \pm 3 days from Target Day (For body weight) Study Day \pm 14 days from Target Day (For waist-hip ratio related parameters) ET visits are mapped to the nearest missing analysis visit, using the same window, after unscheduled visits are considered |
| ECG | Study Day \pm 3 days from Target Day ; ET visits are mapped to the nearest missing analysis visit after unscheduled visits are considered using Study Day |
| PK | Depending on the time point, the window for each time point is specified in the PK sampling schedule. If multiple unscheduled records are available, the sample collected closest to the nominal time will be selected. If the distance is the same, the later one will be selected. (Actual time should be used for PK analysis) |

Measurements from all protocol planned visits will be summarized in descriptive tables and figures. For pharmacodynamic endpoints that are analyzed using MMRM analysis, only measurements taken at weekly analysis visits (eg, Day 1, Day 8, 15, 22, 29, 36, etc) will be included in the analysis and corresponding data presentation. Analyses will utilize the measurements taken at the scheduled visits whenever they are available. If not available, the analysis will use the measurement mapped to that scheduled visit (whichever is the closest to the target date, and if there are two measurement before and after the target day with same duration, use the measurement taken at the later day) If there are duplicate results from the same sample are available, eg, with the identical sampling date and time, the average value will be used for data analysis and both raw data and average value will be listed. EOS/ET visits will be summarized in descriptive summary. ET visits will be eligible to be mapped to missing protocol planned visits, but will not on its own be considered an analysis visit or time point.

9.1.4. Assessments Below and Above the Limit of Quantification

For summarization of PK concentration values and data analysis, assessments that are below the lower limit of quantification (LLOQ) will be set to zero prior to summarization. For PK concentration graphs, assessments that are below the lower limit of quantification will be set to half of LLOQ prior to graphing. For PK concentration assessments that are above the upper limit of quantification (ULOQ), the record will be set to missing prior to summarization or graphing. For other exploratory PK analysis such as population PK, assessment that are below the LLOQ may be defined differently.

For all other assessments that are below the lower limit of quantification will be imputed to half of the LLOQ for summarization; assessments that are above the upper limit of quantification will be imputed to the ULOQ for summarization.

For listings, records that are LLOQ or ULOQ will be listed as such together with the imputed value in separate columns.

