4.1.2. Pharmacokinetic Endpoints

The primary pharmacokinetic endpoints are:

- Maximum concentration (C_{max}) on Day 1
- C_{max} on Day 29
- Area under the curve since last dose ($AUC_{0-\tau}$) on Day 1
- $AUC_{0-\tau}$ on Day 29
- Time to maximum concentration (t_{max}) on Day 1
- t_{max} on Day 29
- Half-life ($t_{1/2}$) on Day 1
- $t_{1/2}$ on Day 29

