9.2.1. Analysis of Serum Concentrations of BIO89-100

The serum concentration of BIO89-100 over time will be listed and plotted by individual and also summarized by treatment group. Serum concentration data will also be presented using arithmetic statistics.

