9.2.2. Analysis of PK Parameters

The following PK endpoints will be summarized by treatment group:

- C_{max} within a dosing interval (Day 1 and Day 29), the maximum serum concentration within each dosing interval.
- $AUC_{0-\tau}$ within a dosing interval (Day 1 and Day 29), derived using linear-log trapezoidal rule; assuming linear curve when concentrations are increasing and exponential decay when concentrations are decreasing.
- t_{max} , the time at which C_{max} is observed in reference to the start of the dosing interval during dosing interval (Day 1 and Day 29).
- $t_{1/2}$, the time at which the concentration is half of the observed maximum concentration within the dosing interval during dosing interval (Day 1 and Day 29).

PK parameters will be calculated separately by designee of 89bio.

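### Both SAPs delete serum drug concentrations above the ULOQ from PK summaries and graphs, which biases those summaries downward whenever such a record occurs; the rule for deriving Cmax and AUC is not stated.

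*SAP*

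**What the plan says.** Section 9.1.4 of the Part 1 SAP treats drug concentrations and all other assays differently.

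- **PK, below the lower limit (LLOQ).** The paragraph opens "For summarization of PK concentration values and data analysis" and sets such values to zero (half the LLOQ in graphs).
- **PK, above the ULOQ.** "the record will be set to missing prior to summarization or graphing".
- **All other assessments, above the ULOQ.** "assessments that are above the upper limit of quantification will be imputed to the ULOQ for summarization".
- **Listings.** "records that are LLOQ or ULOQ will be listed as such together with the imputed value in separate columns".

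Section 8.1.4 of the Part 2 SAP repeats these rules.

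The rule acts on the following outputs. In Part 1, section 9.2.1 has concentrations listed and plotted by individual and summarized by treatment group: "Serum concentration data will also be presented using arithmetic statistics". In Part 2, section 8.2 summarizes and plots trough concentrations by visit.

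Cmax and AUC over the dosing interval, on Day 1 and Day 29, are in the Part 1 SAP list in section 4.1.2 that begins "The primary pharmacokinetic endpoints are". Section 9.2.2 defines Cmax as "the maximum serum concentration within each dosing interval" and adds: "PK parameters will be calculated separately by designee of 89bio". Neither SAP nor the protocol gives a ULOQ, an expected share of samples above it, or a dilution and re-assay rule.

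**The concern.** A concentration reported as above the ULOQ is not an unknown value: it is known to be at least the ULOQ. Setting it to missing makes missingness depend on the value itself, and only the largest values are lost. The retained records are then a truncated sample, and their mean must be lower than the mean of all records. An individual curve shows a gap or a false, lower peak where the highest exposure was.

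The plan applies this harsher rule to the study drug itself and gives no reason, although the same section keeps the information for every other assay. The LLOQ rule does not offset the loss, because setting low values to zero also tends to lower the mean.

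At stake are the descriptive concentration tables and graphs in both parts. Part 2 is less likely to be affected, because its PK endpoint is the trough, where values above the ULOQ are least expected. Cmax and AUC matter more, as primary Part 1 endpoints, but the text does not say whether the deletion reaches them.

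**Working it through.** The plan states no figure on this point, so there is nothing to reproduce. The direction follows from the rule; the size needs assumptions.

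**Direction.** Every deleted value exceeds every retained value, so if any record is deleted the mean of the remainder is strictly lower. The median and maximum can only stay the same or fall.

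**Size for a concentration mean at one time point.** Assumed, not in the documents: concentrations are lognormal; between-subject CV is 40% or 50%; a share p of 10% or 20% of records exceeds the ULOQ; no re-assay result is available. Scale the true mean to 1 and write

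- s = √ln(1 + CV²), and z = Φ⁻¹(1 − p)
- ULOQ relative to the true mean: u = exp(s·z − s²/2)
- mean after deletion = Φ(z − s) / (1 − p)
- mean after setting to the ULOQ = Φ(z − s) + p·u

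Worked case, CV 40% and p = 10%: s = √ln 1.16 = 0.385; z = 1.282; z − s = 0.896; Φ(0.896) = 0.815; u = 1.521. Deletion gives 0.815 / 0.9 = 0.906, which is 9.4% low. Setting to the ULOQ gives 0.815 + 0.1 × 1.521 = 0.967, which is 3.3% low.

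| CV | Share above ULOQ | Φ(z − s) | u | Deleted | Set to ULOQ |
|---|---|---|---|---|---|
| 40% | 10% | 0.815 | 1.521 | −9.4% | −3.3% |
| 40% | 20% | 0.676 | 1.284 | −15.5% | −6.7% |
| 50% | 10% | 0.791 | 1.639 | −12.1% | −4.5% |
| 50% | 20% | 0.644 | 1.331 | −19.5% | −9.0% |

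**Wider range.** Over CV 30–80%, with 5% of records above the ULOQ, deletion leaves the mean 4.0–13.0% low and setting to the ULOQ 1.1–4.9% low. With 20% above, the ranges are 11.5–30.6% and 4.7–16.3%. With none above, both are zero.

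**Cmax, only if the deletion were carried into its derivation.** No reported Cmax could then exceed the ULOQ. A simulated one-compartment subcutaneous profile shows the order of size. Its absorption rate (0.05/h), half-life (70 h) and sampling times (0 to 168 h) are all assumed, since the actual times are redacted. With CV 50% and 10% of subjects having a peak above the ULOQ, mean Cmax is 6.7% low under deletion and 4.7% low if set to the ULOQ. Among the affected subjects, deletion lowers Cmax by about 31%. This illustrates a conditional risk; it does not describe what the plan does.

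**The case against.** The strongest reply is that the rule may never matter. The documents give no sign that any final result will exceed the ULOQ, and the 10–20% share is assumed. Assays are run by the bioanalytical laboratory, so a SAP without a dilution rule does not show that high samples go without a re-assay. If they receive a numeric result, there is no bias. This stands, and it makes the point conditional. It does not make the rule sound, because the rule operates only when such a record exists, and it is then biased.

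A reader might infer three stronger things that the documents do not support.

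- **That Cmax and AUC are biased.** The ULOQ sentence covers summarization and graphing only, whereas the LLOQ sentence also names data analysis. PK parameters are calculated separately by a designee, and protocol section 8 promises a pharmacokinetic analysis plan, which is not among the documents. The plan is silent on this step; it contains no demonstrated error there.
- **That high exposure is hidden.** Records above the ULOQ stay flagged in the listings. They are lost from tables and plots, not from the report.
- **That the safety margins or a dose-proportionality conclusion would change.** Protocol section 3.2.4 builds the margins from the earlier single-dose study and a monkey model, not from these tables. The PK sections of the Part 1 SAP specify no dose-proportionality analysis.

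It is also fair to say that setting values to the ULOQ is itself biased low. The calculations show that this bias is smaller, about 3–9% against 9–20% in the cases above.

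**Conclusion.** The point holds for concentration summaries and graphs. Both SAPs state a rule that biases them downward whenever a final result exceeds the ULOQ, and it is harsher than the rule the same sections use for other assays. The 9–20% shortfall in a mean under deletion, against 3–9% under setting to the ULOQ, rests on lognormal data, CV 40–50% and 10–20% of records affected, none of which the documents give. For Cmax and AUC the finding is an unstated rule, not a shown bias. The change is worth making before database lock because the rule is wrong whenever it is triggered and costs little to correct. It is not a threat to the trial's conclusions on the evidence in these documents.

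**What to change.** In both SAPs (Part 1 section 9.1.4, Part 2 section 8.1.4), replace deletion with the following:

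1. Where a valid diluted re-assay result exists for a sample above the ULOQ, use it.
2. Otherwise set the value to the ULOQ, and flag the affected summary as a lower bound.
3. Report the number of such samples per time point and dose group (per time point in Part 2, which has one dose).

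In Part 1, add to section 9.2.2 that records above the ULOQ are not dropped when Cmax and AUC are derived, and that affected parameters are flagged. The designee's derivation should follow the same rule.

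The cost is a sentence or two in each SAP and one count in the concentration tables. If no sample is affected, nothing changes. The remaining downside is that a mean with values set to the ULOQ is still low, though less so than after deletion; this is why the re-assay result comes first and the flag is needed.
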